7.2 Primary Analysis

7.2.1 Phase 1

The primary analysis for phase 1 will occur when target enrollment in phase 1 dose escalation and dose expansion is complete and each subject either completes 6 months on study or withdraws from the study.

7.2.2 Phase 2

The primary analysis for phase 2 will occur after 105 NSCLC or 60 CRC subjects are enrolled in phase 2 and have 6-month follow-up, whichever group occurs first. The data cutoff was decided to allow sufficient time to demonstrate durability of ORR. Subjects who end the study prior to 6 months will be counted. The data will be analyzed once they have been entered, cleaned, and locked. The primary analysis will summarize for all tumor types even if it is triggered by 105 NSCLC subjects or 60 CRC subjects.

Results from the tumor cohort without sufficient subjects with 6-month follow up will be used descriptively. A subsequent analysis when the prespecified number of subjects in this cohort reach 6 months follow-up is outlined in [Section 7.3.2](#).

7.3 Additional Analysis Subsequent to Primary Analysis

7.3.1 Phase 1

At the time of Phase 2 Primary Analysis, phase 1 analyses will be updated to capture additional durable response after Phase 1 Primary Analysis.

7.3.2 Phase 2

If the primary analysis is triggered by 105 NSCLC (60 CRC) subjects reaching 6-month follow-up, a subsequent analysis will occur when 60 CRC (105 NSCLC) subjects have 6-month follow-up. The data will be analyzed once they have been entered, cleaned, and locked.

7.4 Final Analysis

The final analysis will occur when the end of study as defined in [Section 5](#) has been reached. The data will be analyzed once they have been entered, cleaned, and locked. The purpose of this analysis is to summarize efficacy and safety after all subjects have completed follow-up.

8. Data Screening and Acceptance

8.1 General Principles

The objective of the data screening is to assess the quantity, quality, and statistical characteristics of the data relative to the requirements of the planned analyses.

8.2 Data Handling and Electronic Transfer of Data

The Amgen Global Study Operations-Data Management (GSO-DM) department will provide all data to be used in the planned analyses. This study will use the RAVE database. The database will be subject to edit checks outlined in the Clinical Data Management Plan (DMP). See details of this section in the DMP.

8.3 Handling of Missing and Incomplete Data

Incomplete adverse event and concomitant medication dates missing data will be imputed as described in [Appendix A](#).

8.4 Detection of Bias

Lack of protocol compliance and the potential for biased statistical analyses will be examined by assessing the incidence of important protocol deviations in each cohort. The clinical study team will identify and document the criteria for important protocol deviations.

8.5 Outliers

PK concentration data will be evaluated for outliers by visual inspection, and decisions to re-assay individual samples will be made in accordance with standard PK evaluation practice.

8.6 Distributional Characteristics

Where appropriate, the assumptions underlying the proposed statistical methodologies will be assessed. If required data transformations of analyses will be utilized.

8.7 Validation of Statistical Analyses

Programs will be developed and maintained, and output will be verified in accordance with current risk-based quality control procedures.

Tables, figures, and listings will be produced with validated standard macro programs where standard macros can produce the specified outputs.

The production environment for statistical analyses consists of Amgen-supported versions of statistical analysis software; for example, the SAS System version 9.4 or later.

9. Statistical Methods of Analysis

9.1 General Considerations

Descriptive statistics will be provided for selected demographic, safety and efficacy data. Descriptive statistics on continuous data will include means, medians, standard deviations, minimums & maximums while categorical data will be summarized using frequency counts and percentages. For time-to-event variables, the Kaplan-Meier (KM) estimates and corresponding two-sided 95% confidence intervals for the median and quartiles will be provided. Graphical summaries of the data may also be presented. The K-M plot may also be provided.

Efficacy and safety analyses will pool together all tumor types and also present tumor types separately. Efficacy analysis for Phase 1 and Phase 2 will be analyzed separately. In addition, integrated safety analyses will be done by different planned dose levels and treatments (monotherapy or combination therapy) and phases, using the Safety Analysis Set.

Futility and efficacy thresholds in phase 1 and futility interim in phase 2 will be based on site-assessed disease response per RECIST 1.1. Primary, final, and any additional efficacy analyses will be based on an independent radiologic assessment of disease response per RECIST 1.1.

Nominal 95% confidence intervals will be calculated.

9.2 Subject Accountability

The number and percent of subjects who were enrolled, received investigational product, discontinued from investigational product (including reasons for discontinuing, completed study, discontinued the study (including reasons for discontinuing) will be summarized. Key study dates for the first subject enrolled, last subject enrolled, and last subject's end of study will be presented.

9.3 Important Protocol Deviations

Important Protocol Deviations (IPDs) categories are defined by the study team before the first subject's initial visit and updated during the IPD reviews throughout the study prior to database lock. These definitions of IPD categories, subcategory codes, and descriptions will be used during the study. The final IPD list is used to produce the Summary of IPDs table and the List of Subjects with IPDs. In addition, a separate listing of all inclusion and exclusion deviations will be provided.

9.4 Demographic and Baseline Characteristics

The following descriptive summaries of the demographic and baseline characteristics will be produced:

- Race: (White, Asian, Black or African American, vs other categories depending on frequency observed) If multiple races have been reported for a subject, the subject will be categorized as multiple.
- Gender: (male vs. female)
- Age at enrollment categories (< 65 vs. ≥ 65)
- Age at enrollment in years (summary statistics)
- Baseline weight (summary statistics)
- ECOG Performance Status at baseline (0 vs. 1)
- Time from initial diagnosis to enrollment
- Primary tumor location (NSCLC, CRC vs other tumor types)
- Disease Stage at Initial Diagnosis (I, II, III, IV)
- Disease Stage at Screening (I, II, III, IV)
- Histopathology Type (Adenocarcinoma, squamous cell carcinoma, Large cell carcinoma, Bronchoalveolar carcinoma, undifferentiated, other)
- Prior lines of therapy (0, 1, 2)
- Prior anti-cancer therapy for current malignancy (yes, no)
- Response to prior anti-cancer (yes, no)
- Prior radiotherapy for current malignancy (yes, no)
- Prior surgery for current malignancy (yes, no)

- Number of metastatic sites (0, 1, 2 or more)
- Brain metastases (yes, no)
- Liver metastases (yes, no)
- History of tobacco use (yes, no)
- ECHO or MUGA, if available

9.5 Efficacy Analyses

Table 8. Phase 1 Efficacy Endpoint Summary Table

Endpoint	Primary Summary and Analysis Method	Analysis Set	Sensitivity Analysis
Primary Endpoint			
None	-	-	-
Secondary Endpoint			
ORR	The percentage of subjects with an OR will be summarized along with a Clopper-Pearson exact confidence interval. Subjects without a post-baseline tumor assessment will be considered non-responders.	Interim during dose expansion: P1OAS Primary and Final: P1FAS	None
DOR	Kaplan-Meier quartiles and rates for select durations (eg, > 3, > 6, > 9, > 12 months)	P1FAS	None
DCR	The percentage of subjects with disease control will be summarized along with a Clopper-Pearson exact confidence interval. Subjects without a post-baseline tumor assessment will be considered non-responders.	P1FAS	None
Duration of stable disease	Kaplan-Meier quartiles and rates for select durations (eg, > 3, > 6, > 9, > 12 months)	P1FAS	None
PFS	Kaplan-Meier curves, quartiles, and rates for select timepoints (eg, 6 and 12 months)	P1FAS	None

P1OAS = Phase 1 monotherapy RP2D ORR Analysis Set. P1FAS = Phase 1 Full Analysis Set

Table 9. Phase 2 Efficacy Endpoint Summary Table

Endpoint	Primary Summary and Analysis Method	Analysis Set	Sensitivity Analysis
Primary Endpoint			
ORR	The percentage of subjects with an OR in Phase 2 ORR Analysis Set will be summarized along with a Clopper-Pearson exact confidence interval. Subjects without a post-baseline tumor assessment will be considered non-responders.	P2OAS	None
Secondary Endpoints			
DOR	Kaplan-Meier quartiles and rates for select durations (eg, > 3, > 6, > 9, > 12 months)	P2OAS	None
DCR	The percentage of subjects with disease control will be summarized along with a Clopper-Pearson exact confidence interval. Subjects without a post-baseline tumor assessment will be considered non-responders.	P2FAS	None
OS	Kaplan-Meier curves, quartiles, and rates for select timepoints (eg, 6 and 12 months)	P2FAS	None
PFS	Kaplan-Meier curves, quartiles, and rates for select timepoints (eg, 6 and 12 months)	P2FAS	None
TTR	Summary of non-missing sample size (n), mean, standard deviation, median, minimum, and maximum for responders	P2OAS	None

P2OAS = Phase 2 ORR Analysis Set. P2FAS = Phase 2 Full Analysis Set

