10.1.1.2.2 Secondary Endpoints

- DOR - defined as time from first evidence of confirmed PR or CR to disease progression or death due to any cause, whichever occurs first. Subjects without a duration ending event will be censored at their last evaluable disease assessment date. Progression will be based on an independent radiologic assessment of disease response per **RECIST** 1.1.
- DCR defined as CR + PR + stable disease rate measured as described for ORR.
- PFS - defined as time from first dose of AMG 510 until disease progression or death from any cause, whichever occurs first. Subjects who do not progress or die will be censored at their last evaluable disease assessment date. Progression will be on an independent radiologic assessment of disease response per **RECIST** 1.1.
- OS - defined as time from first dose of AMG 510 until death from any cause. Subjects who do not die will be censored at the date of last contact.
- PFS rate at 6 months and 12 months.
- OS rate at 12 months.
- Incidence and severity of adverse events.
- PK parameters of AMG 510 including, but not limited to, C_{max} , t_{max} , and AUC.
- **TTR - defined as time from first dose of AMG 510 until the first evidence of confirmed PR or CR.**

Approved

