10.1.2.4 Phase 2 Full Analysis Set

The phase 2 full analysis set (P2FAS) will consist of all phase 2 subjects who received at least 1 dose of AMG 510. The primary analysis (excluding the analysis of ORR) and the final analysis will be performed on the P2FAS.

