6.1.2 Phase 2 Full Analysis Set

The phase 2 full analysis set (P2FAS) will consist of all subjects that are enrolled in phase 2 and receive at least 1 dose of AMG 510. The analysis of safety, PFS, and OS for Phase 2 will be performed on the P2FAS.

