6.7.3 Phase 2 ORR Analysis Set

The phase 2 ORR analysis set (P2OAS) will consist of all subjects in the phase 2 full analysis set who have had at least 6 weeks response data starting from day 1. Subjects who stopped disease assessments prior to 6 weeks will be included in this analysis set if the data cutoff is at least 6 weeks after their first dose date. The interim futility analysis, primary analysis, and final analysis of ORR, DOR, and TTR will be performed on the P2OAS.

7. Planned Analyses

The following interim, primary, and final analyses for phase 1 and phase 2 portions of the study are planned.

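### Phase 2 DCR is set on all dosed subjects while ORR needs 6 weeks of data, so at the primary analysis recently dosed subjects pull DCR down in cohorts still enrolling

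*Supplement*

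**What the plan says.** The current documents are Protocol Amendment 3 and SAP Amendment 1.

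- **DCR rule.** SAP 9.5, Table 9, phase 2 DCR row: "The percentage of subjects with disease control will be summarized along with a Clopper-Pearson exact confidence interval", followed by "Subjects without a post-baseline tumor assessment will be considered non-responders". The analysis set is the P2FAS, and the sensitivity analysis column reads none.
- **P2FAS.** SAP 6.1.2 defines it as "all subjects that are enrolled in phase 2 and receive at least 1 dose of AMG 510". It then names safety, PFS and OS as the analyses done on it. DCR is not named.
- **P2OAS.** SAP 6.7.3 restricts it to "subjects in the phase 2 full analysis set who have had at least 6 weeks response data starting from day 1". Subjects who stopped assessments early are kept if first dosed at least 6 weeks before cutoff. It continues: "The interim futility analysis, primary analysis, and final analysis of ORR, DOR, and TTR will be performed on the P2OAS". DCR is not named here either.
- **Protocol.** Section 10.1.2.4 says "The primary analysis (excluding the analysis of ORR) and the final analysis will be performed on the P2FAS". Section 10.1.1.2.2 says "DCR defined as CR + PR + stable disease rate measured as described for ORR".
- **Stable disease.** SAP section 5 requires imaging no earlier than 6 weeks after cycle 1 day 1 for a best response of SD, and otherwise classifies the subject as not evaluable. Its DCR definition uses SD beyond 6 weeks.
- **Timing.** SAP 7.2.2 triggers the phase 2 primary analysis when either 105 NSCLC or 60 CRC subjects have 6 months of follow-up. It adds: "The primary analysis will summarize for all tumor types even if it is triggered by 105 NSCLC subjects or 60 CRC subjects". SAP 9.1 pools tumor types as well as presenting them separately.

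**The concern.** A full analysis set suits PFS and OS because censoring handles short follow-up. A binomial proportion has no such mechanism. A subject dosed three weeks before cutoff has no scan due, yet is scored as a disease-control failure, so calendar timing is recorded as lack of effect.

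Such subjects are foreseeable. One cohort triggers the analysis but every cohort is reported. Enrolment start may be gated by tumor type (SAP 3.1). CRC enrolment pauses at its first futility look and NSCLC enrolment does not (SAP 7.1.3.2).

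At stake is a secondary rate that depends on recruitment timing and sits beside an ORR with a different denominator. Every responder has disease control, so a reader expects DCR to be at least as large as ORR. With mixed denominators that is not guaranteed.

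**Working it through.** **1. The plan's own figures.** The documents give no figure for DCR. The nearest one using the same exact method is the minimum observed ORR in Protocol 10.2.2: 32% of 105 NSCLC and 20% of 60 CRC. Both reproduce with two-sided 95% Clopper-Pearson limits:
- NSCLC, benchmark 23%: 34/105 = 32.4% has lower limit 23.6%; 33/105 has 22.7% and fails.
- CRC, benchmark 10%: 12/60 = 20.0% has lower limit 10.8%; 11/60 has 9.5% and fails.

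**2. How one recent subject is counted.** Take a subject first dosed less than 6 weeks before cutoff and still on study. The scan schedule is every 6 ± 1 weeks. SD cannot be assigned before 6 weeks, and CR or PR needs a repeat scan about 4 weeks after detection. Under the scheduled scans the subject cannot be CR, PR or SD.
- DCR on P2FAS: denominator +1, numerator +0.
- ORR on P2OAS: denominator +0, numerator +0.

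**3. Formula.** Let N be the number dosed, k the number of recent subjects, and D the disease-control proportion among the other N − k.
- P2OAS rate = D
- P2FAS rate = D × (N − k)/N
- Shortfall = D × k/N

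**4. Size.** Neither D nor k is in the documents, so both are assumed. The smallest corner is 0.50 × 0.05 = 2.5 points and the largest is 0.90 × 0.20 = 18 points. With D near 80%:

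| N | k | DCR on P2OAS | DCR on P2FAS | Shortfall (points) |
|---|---|---|---|---|
| 60 | 3 | 46/57 = 80.7% | 46/60 = 76.7% | 4.0 |
| 60 | 6 | 43/54 = 79.6% | 43/60 = 71.7% | 8.0 |
| 60 | 12 | 38/48 = 79.2% | 38/60 = 63.3% | 15.8 |
| 200 (pool) | 10 | 152/190 = 80.0% | 152/200 = 76.0% | 4.0 |
| 200 (pool) | 20 | 144/180 = 80.0% | 144/200 = 72.0% | 8.0 |
| 200 (pool) | 40 | 128/160 = 80.0% | 128/200 = 64.0% | 16.0 |

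In the last row the exact 95% intervals do not overlap: 73.0% to 85.9% on the P2OAS and 56.9% to 70.6% on the P2FAS.

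**5. Comparison with ORR.** In a constructed case with N = 60 and k = 18, 15 responders give ORR 15/42 = 35.7%, while 21 subjects with disease control give DCR 21/60 = 35.0%. DCR is then reported below ORR. On a common denominator DCR would be 21/42 = 50.0%.

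**The case against.** Much of the mitigation is already in the SAP, and it stands. SAP 7.2.2 calls results from the cohort without enough 6-month follow-up descriptive. SAP 7.3.2 repeats the NSCLC or CRC analysis when that cohort reaches its own 6 months. The final analysis (SAP 7.4) follows completed follow-up, when no subject is recent. DCR is secondary, with no benchmark, power or decision rule, and the bias is downward, so it cannot flatter the drug.

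Three stronger readings are tempting, and the documents do not support them.

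- **That the triggering cohort is hit as hard.** The 105 or 60 that trigger the analysis have 6 months of follow-up or have ended study. For NSCLC to contain recent subjects, enrolment must run on for about 20 weeks after the 105th (26 − 6). At an assumed 10 per 6 weeks, about 33 more would enrol in between and be assessable. The cohort would be 105 + 33 + 10 = 148, and with 60 CRC that is 208, above the planned approximately 200. An 80% DCR would read 0.80 × 138/148 = 74.6%. The targets are stated as minimums, so this is possible but not the main case.
- **That every recent subject is a false failure.** Some would have progressed or died anyway. The expected number of false failures is about k × true DCR.
- **That Table 9 contradicts the protocol.** The protocol's wording that DCR is measured as for ORR reads naturally as the method (imaging, RECIST 1.1, independent review), not the denominator. Protocol 10.1.2.4 excludes only ORR from the P2FAS, so the DCR row follows it.

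What survives is the counting rule itself, and the fact that SAP 6.1.2 and 6.7.3 leave DCR unassigned.

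**Conclusion.** The point holds in a limited form. As written, the phase 2 DCR rule gives a downward-biased estimate in any cohort that dosed subjects in the 6 weeks before cutoff, on a different denominator from ORR. The shortfall is about true DCR × k/N: roughly 2.5 to 18 points over the assumed ranges in the working, and zero when k = 0. The documents give no accrual rate from which to narrow this.

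It applies at the phase 2 primary analysis, mainly to the non-triggering cohort, other tumor types and the pooled summary. For NSCLC and CRC it is largely resolved by the later cohort-specific analysis. For other tumor types SAP 7.3.2 names no further analysis before the final one. No efficacy conclusion or stopping decision depends on it. It is worth correcting because the SAP moved DOR and TTR, which are computed only in responders, to the P2OAS, and left on the P2FAS a rate that depends directly on the denominator.

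**What to change.** 1. In SAP Table 9, change the analysis set for phase 2 DCR from P2FAS to P2OAS.
2. Add DCR to the endpoints named in SAP 6.7.3.
3. Record the departure from Protocol 10.1.2.4 in SAP section 10, which now lists only PFS2. The same note can cover DOR and TTR. Align the protocol text at its next planned amendment; a separate amendment needing ethics approval is not warranted for this alone.

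If the sponsor prefers to keep the P2FAS, the minimum is to replace the empty sensitivity entry in that row with DCR on the P2OAS.

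The cost is a table cell, one added item and a short note, with no new data. There is a small downside: DCR at the primary analysis would leave out recently dosed subjects and depart from the protocol's stated set. Early failures are not dropped, because the P2OAS keeps subjects who stopped assessments early if first dosed at least 6 weeks before cutoff, and those without a scan still count as failures.

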9.5.1 Analyses of Primary Efficacy Endpoint(s)

The number and percentage of subjects with a best overall response of Complete Response (CR), Partial Response (PR), Stable Disease (SD), Progressive Disease (PD), Not Evaluable (NE) will be presented. ORR will be summarized along with a Clopper-Pearson exact 95% confidence interval ([Clopper and Pearson, 1934](#)). Subjects without a post-baseline tumor assessment will be considered non-responders.

9.5.2 Analyses of Secondary Efficacy Endpoint(s)

DOR will be calculated only for subjects who achieve a best overall response of PR or better. Subjects will be censored following the censoring strategy described in the definition of PFS time in [Table 1](#). The distribution of DOR, including the median and quartiles will be characterized using the Kaplan-Meier(KM) method based on the subjects who achieve a best response of PR or better. The 95% CIs for the median and

quartiles of PFS will be constructed using the method of [Klein and Moeschberger \(1997\)](#) with log-log transformation. The rates for select durations (eg, > 3, > 6, > 9, > 12 months) will be reported. The 95% CIs for PFS rates will be estimated using the methods by [Kalbfleisch and Prentice \(1980\)](#) with log-log transformation. KM curve can be done for DOR if at least 10 subjects have a CR/PR.

The proportion of subjects with disease control (CR, PR or SD > 6 weeks) with corresponding exact 95% CI will be calculated using the Clopper-Pearson method.

Duration of Stable Disease will be analyzed using the same method as describe for DOR.

The distribution of PFS, including median, will be estimated using the Kaplan-Meier method. PFS rate at the selected time points (6 months and 12 months) will be reported. The 95% CIs for the median and other percentiles of PFS will be constructed using the method of [Klein and Moeschberger \(1997\)](#) with log-log transformation. The 95% CIs for PFS rates will be estimated using the methods by [Kalbfleisch and Prentice \(1980\)](#) with log-log transformation.

OS will be analyzed using the same method as describe for the PFS endpoints.

Time to response will be summarized with the non-missing sample size (n), mean, standard deviation, median, minimum, and maximum for responders, ie, subjects who achieve best overall response of sCR, CR, BGPR, or PR.

9.5.3 Analyses of Exploratory Efficacy Endpoint(s)

PFS2 is defined as time from start of the treatment to objective disease progression on next-line treatment or death from any cause, whichever occurs first. If the date of the second disease progression is not available, then the start date of the next line of therapy following the second disease progression will be used as the surrogate for the date of the second disease progression and it will be considered as a PFS2 event. For a subject who is alive and without second disease progression date or the start date of the next line of therapy, PFS2 will be right-censored at the date on which the subject is last known to be alive. The analysis method will be the same as that for the PFS and OS analysis.

9.6 Safety Analyses

9.6.1 Analyses of Primary Safety Endpoint(s)

Unless otherwise specified, statistical analyses on safety endpoints in Phase 1 will be done using subjects from the Phase 1 Full Analysis Set; statistical analyses on safety

endpoint in Phase 2 will be done using subjects from the Phase 2 Full Analysis Set; integrated safety analysis will be done using subjects from integrated Safety Analysis Set, which includes all subjects that are enrolled and received at least 1 dose of AMG 510. DLT analysis will be done using DLT-evaluable subjects.

Subject incidence of DLTs will be used to fit the BLRM model to estimate the probability of having a DLT across dose levels

